#### Confidentiality Statement

---

The confidential information in this document is provided to you as an investigator or consultant for review by you, your staff, and the applicable Institutional Review Board. Your acceptance of this document constitutes agreement that you will not disclose the information contained herein to others without written authorization from the sponsor.

the subject to be eligible to participate in the study. This will allow results confirming no brain pathology, which would include evidence of infection, infarction (including multiple lacunas in a critical memory structure), or other focal lesions to be available for review at the baseline visit. If a history of cerebral aneurysm is suspected, the subject will be referred to their primary physician and/or neurologist.

The exploratory endpoints for this study include:

- Evidence of altered peripheral or cerebrovascular physiology including:
  - The observed value and change from baseline in hippocampal volume measured by MRI at 24 weeks and 12 months after initiation of treatment
  - Changes from baseline to 24 weeks after initiation of treatment or active sham in:
    - **Cerebral blood flow (CBF) in multiple regions (hippocampus, precuneus, parietal, inferior frontal lobe) measured by arterial spin labeling** between the treatment and active sham groups from screening, to 24 weeks and 12 months (selected sites only);
    - **Global cerebral blood flow as measured via MRI**
    - White matter hyperintensities as **measured via MRI**
    - **CBF velocity in cerebral arteries as measured by Transcranial Doppler at baseline, 12 and 24 weeks (selected sites only)**
    - **Endothelial function via flow-mediated dilation (FMD) (brachial or femoral), as measured by ultrasound at baseline, 12 and 24 weeks (selected sites only)**
    - **Arterial stiffness via pulse wave velocity (PWV)** measured by arterial tomography or ultrasound at baseline, 12 and 24 weeks (selected sites only)
    - **Arterial stiffness via augmentation index** measured by arterial tomography at baseline, 12 and 24 weeks
    - **Deep tissue oxygenation** (hemoglobin concentration and SO2) via near infrared spectroscopy at baseline, 12 and 24 weeks
    - **Blood viscosity** at baseline, 12 and 24 weeks (selected sites only)
    - **Lipid panel:** total cholesterol, LDL-C, HDL-C, triglycerides, Blood fibrinogen at baseline, 12 and 24 weeks
    - **Inflammatory markers:** C-Reactive Protein (CRP), Lp-PLA2 and MPOS at baseline, 12 and 24 weeks
    - **CBC:** including Red Cell Distribution Width (RDW) & Hemoglobin at baseline, 12 and 24 weeks
    - **Presence**
- **Difference in change from baseline** at 12 and 24 weeks in the **Behavioral Assessment** measured via Neuropsychiatric Inventory (NPI) Agitation/Aggression.

---

Confidentiality Statement

---

The confidential information in this document is provided to you as an investigator or consultant for review by you, your staff, and the applicable Institutional Review Board. Your acceptance of this document constitutes agreement that you will not disclose the information contained herein to others without written authorization from the sponsor.

- **Difference in change from baseline** at 12 and 24 weeks in **balance, functional mobility, and fall-risk assessment measured via Timed Up & Go (TUG) test and the Functional Reach Test.**
- **Time course comparative analysis** between treatment and active sham groups in **ADAS Delayed Word Recall** (a sub-test of the vADAS cog) at baseline, 12 and 24 weeks.
- **Time course comparative analysis** between treatment and active sham groups in **ADAS Word Recognition** (a sub-test of the vADAS-cog) at baseline, 12 and 24 weeks.
- **Comparison of ADAS-Cog12 scores at 12 weeks, 24 weeks, 9 months, and 12 months between an external control arm of digital twins and each of the actual treatment and active sham groups.** An external control arm of digital twins (digital subjects with the same baseline characteristics as actual study participants) simulates, at a subject level, clinical trajectories of actual study subjects under the counterfactual scenario of no treatment. Ten digital twins will be created for each subject enrolled in the study. The digital twins will be generated by a model of AD progression developed by Unlearn.AI Inc., based on data from the control arms of 18 AD and MCI phase II and III clinical trials (4897 subjects) (Neville, et al., 2015). This model was shown to generate digital controls which are statistically indistinguishable from those of actual control subjects across a wide variety of clinical measures included in the model (Fisher, et al., 2019; Walsh, et al., 2020). The treatment effect vs. external control group will be estimated for each of the actual study arms (treatment and active sham), including testing the hypothesis that there is no treatment effect in the active sham arm vs. external control arm.

## 6. STUDY ENROLLMENT AND WITHDRAWAL

### 6.1 Inclusion Criteria

Subjects will meet all inclusion criteria and none of the exclusion criterion. The study is open to both genders and members of all minority groups. Subjects enrolled into the study will:

1. Be 55-85 years of age at the time of signing the informed consent
2. Be able to provide consent or have legally authorized representative/caregiver who can provide consent
3. Be able to read and write in English or Spanish
4. Have a clinical diagnosis consistent with 2011 NIA-AA “core clinical criteria” guidelines for: (i) The diagnosis of dementia due to Alzheimer’s disease or (ii) The diagnosis of mild cognitive impairment due to Alzheimer’s disease:
  - MOCA score of greater than or equal to 11
  - All required checkboxes within the study checklist for “The diagnosis of probable AD dementia” must be “yes” or

---

#### Confidentiality Statement

---

The confidential information in this document is provided to you as an investigator or consultant for review by you, your staff, and the applicable Institutional Review Board. Your acceptance of this document constitutes agreement that you will not disclose the information contained herein to others without written authorization from the sponsor.

- All required checkboxes within the study checklist for “The diagnosis of mild cognitive impairment due to Alzheimer’s disease” must be “yes”
5. Stable medications for past 30 days and plan to remain on stable medications for the first 24 weeks of study participation for treatment of chronic conditions
  6. Subject should have a caregiver, study partner or companion (which can be a domestic party) who can complete the study assessments. The assessments may be conducted over the phone if they don’t accompany the participant
  7. Must have the potential to improve by at least 2 points or more in the vADAS-COG

## 6.2 Exclusion criteria

Subjects who meet any of the exclusion criteria will be excluded from study participation. The investigator shall exclude subjects with the following conditions:

1. Unwilling or unable to participate in study procedures
2. Weight >297 lbs. or >135 kg at screening
3. Major confounding neurodegenerative or psychiatric disorder unrelated to the condition under study, including:
  - a. History of clinically-evident stroke
  - b. Current uncontrolled epileptic seizures or epilepsy
  - c. Multiple Sclerosis or Parkinson’s Disease
  - d. Current clinically significant major psychiatric disorder (e.g., Major Depressive Disorder) according to DSM-V criteria or significant psychiatric symptoms (e.g., hallucinations) that could impair the completion of the study
4. Anyone with active or history of cerebral hemorrhage including subdural & subarachnoid or cerebral aneurysm
5. Evidence of any of the following (based on Section 4.1.1(D) of the 2011 NIA-AA guidelines on The diagnosis of dementia due to Alzheimer’s disease):
  - a. Substantial concomitant cerebrovascular disease, defined by a history of a stroke temporally related to the onset or worsening of cognitive impairment; or the presence of multiple or extensive infarcts or severe white matter hyperintensity burden
  - b. Core features of Dementia with Lewy bodies other than dementia itself
  - c. Prominent features of behavioral variant frontotemporal dementia
  - d. Prominent features of semantic variant primary progressive aphasia or nonfluent/agrammatic variant primary progressive aphasia
  - e. Evidence for another concurrent, active neurological disease, non-neurological medical comorbidity or use of medication that could have a substantial effect on cognition
6. In the opinion of the investigator, any current clinically-significant systemic illness or medical condition that is likely to result in deterioration of the subject’s condition, affect the subject’s safety during the study, or to be incompatible with performance of the study procedures, including:

---

### Confidentiality Statement

---

The confidential information in this document is provided to you as an investigator or consultant for review by you, your staff, and the applicable Institutional Review Board. Your acceptance of this document constitutes agreement that you will not disclose the information contained herein to others without written authorization from the sponsor.

- a. History of head trauma with a diagnosis of moderate to severe traumatic brain injury
  - b. Known current substantially elevated intracranial pressure
  - c. Known current significant sleep deprivation
  - d. Known history (within five years) or current significant drug abuse or alcoholism
7. Any contraindication for MRI such as insulin pumps or pacemakers, including dual chamber pacemakers where atrial pacing may interfere with Renew™ NCP-5 inflation timing sequence
  8. Hypotension as defined as <80/50 blood pressure at the time of screening
  9. Ongoing uncontrolled severe hypertension ( $\geq 180$  mmHg systolic or  $\geq 110$  mmHg diastolic)
  10. Heart rates < 35 or >125 beats per minute (BPM) at screening
  11. Current uncontrolled arrhythmia. Controlled arrhythmia should have beat-to-beat, cycle-length variability less than  $\pm 25\%$  at rest.
  12. Current congestive heart failure
  13. Cardiac catheterization within two weeks, any surgical intervention within six weeks before Renew™ NCP-5 treatment or a hip or knee replacement within 3 months as long as rehab is complete and symptoms have resolved
  14. Known presence of abdominal aortic aneurysm
  15. Existing aortic insufficiency grade II or higher (regurgitation can prevent diastolic augmentation)
  16. Current or past venous thrombosis or thromboembolism
  17. Current limiting peripheral vascular disease with history strongly suggestive of lower extremity ischemia or claudication, arterial occlusive disease (aortoiliac, ileofemoral, or femoral popliteal)
  18. Demonstrable deficiency in sensation in lower extremities as a result of diabetes or other medical condition
  19. Current bleeding disorders
  20. Current use of major anti-coagulation therapy (such as Heparin therapy or Coumadin® therapy) with INR > 1.5
  21. Current severe pulmonary disease that prevents the subject from lying supine
  22. Presence of local infection, vasculitis, burn, open wound, or bone fracture on any limb which would prevent the ability to perform the Renew™ NCP-5 treatment
  23. Current use of medications that in the investigator's judgement are incompatible with the study goals
  24. Significant changes in existing medical plans for treatment of cognitive impairment or dementia in last three months and/or or planned changes during the trial
  25. Presence of any of the contraindications for using the Renew™ NCP-5 device
  26. Athletic injuries, including Charley horses, pulled muscles and/or edematous muscles; necrotizing cellulitis in the past 30 days which would prevent the ability to perform the Renew™ NCP-5 treatment (evaluate and treat prior to Renew™ NCP-5 treatment)
  27. Unwilling or unable to maintain stable exercise regimen throughout the trial
  28. Participation in any clinical drug trial 30 days or five half-lives, whichever is longer, prior to screening visit

---

Confidentiality Statement

---

The confidential information in this document is provided to you as an investigator or consultant for review by you, your staff, and the applicable Institutional Review Board. Your acceptance of this document constitutes agreement that you will not disclose the information contained herein to others without written authorization from the sponsor.

29. Use of any device to increase cerebral blood flow in the past 30 days
30. History of claustrophobia
31. Subject unable to lay supine for 90 minutes

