AD presents as neurological degeneration that disrupts neuron-to-neuron communication and leads to cell death. Neurological degeneration and cell death, however, will not place AD patients at a greater risk than other populations undergoing Renew™ NCP-5 treatment. While patients with AD often have several comorbidities, primarily due to the more advanced age of the AD population, the study screening process will effectively exclude conditions that may place a subject at a higher risk during Renew™ NCP-5 treatment. This will include subjects with congestive heart failure, deep vein thrombosis, elevated heart rate, heart valve disease, and untreated high blood pressure, among others. Study subjects with these conditions, who are at a greater risk during Renew™ NCP-5 treatment, will be excluded from the study. Moreover, study subjects will not need to terminate their current treatment regimen in order to participate in the study, except under limited circumstances. Subjects will thus not be subject to heightened risk that may be associated with the termination of their current treatment regimen.

The conclusion that treatment with the Renew™ NCP-5 External Counterpulsation System does not present a serious risk to health is supported by the academic literature and historical safe use of Renew™ NCP-5 therapy. The physical symptoms of mild AD, neurological degeneration and cell death, will not place subjects at a heightened risk. In addition, comorbidities found in the AD population that would subject a patient to heightened risk during Renew™ NCP-5 will be excluded during the screening process. Given that Renew™ NCP-5 has been used in medical treatment for over 50 years, the conditions that heighten patient risk during Renew™ NCP-5 treatment are well established and are reflected in the study protocol. Moreover, patients will be required to maintain their current treatment regimen during participation in the proposed study.

Specifically, minor adverse events reported from the use of the Renew™ NCP-5 External Counterpulsation System and approaches to mitigating the risks are as follows:

- Skin irritation, abrasions, bruising and breakdown around the areas on which the device is placed has been reported but are transient. Fabric sleeves can be used under the

---

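### Exclusion 13 has the wrong connective for hip or knee replacement: between six weeks and 3 months after surgery it bars recovered patients and does not itself bar unrecovered ones

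*Protocol*

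**What the plan says.** Section 6.2 of the protocol opens with the rule that governs the whole list: "Subjects who meet any of the exclusion criteria will be excluded from study participation". Meeting one item is therefore enough.

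Item 13 has three limbs. The first is recent cardiac catheterization. The second is "any surgical intervention within six weeks before Renew™ NCP-5 treatment", with no allowance for how well the patient has recovered. The third is "a hip or knee replacement within 3 months as long as rehab is complete and symptoms have resolved".

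Section 3.1 leans on these criteria for the safety case, stating that "the study screening process will effectively exclude conditions that may place a subject at a higher risk" during treatment. Section 7.5 places the cuffs on the calf, lower thigh and buttocks, with a goal of 3-6 PSI or the highest tolerable pressure. Nothing else in the protocol restates or corrects the joint replacement rule.

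**The concern.** Everything in section 6.2 is a reason to keep someone out. A phrase that begins *as long as* therefore limits when the reason applies: the replacement excludes the patient provided that rehabilitation is finished and symptoms are gone. No safety rationale would produce that rule. It reads like permission wording, of the kind used for a patient who is acceptable once healed, placed inside an exclusion sentence.

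Item 13 is the only criterion in the protocol that names joint replacement, and the device compresses the leg on either side of the knee and next to the hip. As written, the criterion fails to do its protective job for part of the group it was meant to cover. Up to 16 sites, treating subjects aged 55 to 85, must each work out the intended rule. They may decide differently about the same kind of patient, or disagree about whether an enrolment was a deviation.

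**Working it through.** No power, alpha or sample size figure is involved, so the check is one of logic plus the width of the affected window.

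**Inputs.** All come from section 6.2: the lead sentence (any one item excludes), the six-week general surgery limb of item 13, and the 3-month joint replacement limb of item 13.

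**Step 1: item 13 read literally, for a patient with a hip or knee replacement**

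| Time from replacement to first treatment | Recovered | Not recovered |
|---|---|---|
| Up to six weeks | Excluded (general surgery limb) | Excluded (general surgery limb) |
| Six weeks to 3 months | Excluded | Not excluded by item 13 |
| Over 3 months | Not excluded | Not excluded by item 13 |

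Only the middle row is affected by the connective.

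**Step 2: compare the middle row with the two plausible intents**

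- Intent (a), admit recovered patients only: recovered allowed, unrecovered excluded. The literal text is wrong for both groups.
- Intent (b), exclude everyone for 3 months: both excluded. The literal text is right for recovered patients and wrong for unrecovered ones.

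So the text is wrong for unrecovered patients under either intent. Intent (a) looks likelier. Item 26 also carries an instruction inside an exclusion, "evaluate and treat prior to Renew™ NCP-5 treatment", which shows that the list mixes permissions and directions with its exclusions. But item 13 does not say which is meant.

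**Step 3: width of the window.** Six weeks is 6 × 7 = 42 days. Three calendar months span 89 to 92 days. Counting both limits back from first treatment:

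- shortest: 89 − 42 = 47 days
- longest: 92 − 42 = 50 days

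That is about 7 weeks. It is a span of calendar time, not a number of subjects. The protocol gives no figure for how many of the 100-250 subjects might have had a replacement in that span.

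**Step 4: the middle row after each possible correction**

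| Wording | Recovered | Not recovered |
|---|---|---|
| *Unless* in place of *as long as* | Allowed | Excluded |
| Rider deleted | Excluded | Excluded |

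The first matches intent (a) and the second intent (b). The other two rows do not change under either.

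**The case against.** The best case for leaving this alone has three parts.

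First, no sensible site would follow the literal text. Both plausible intents keep out the unrecovered patient, so in practice the open question is whether a recovered patient may enter, and that concerns lower-risk people. This largely stands. It limits the harm but does not make the sentence right, and it leaves sites guessing about the recovered group.

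Second, other text overlaps. Item 6 covers "In the opinion of the investigator, any current clinically-significant systemic illness or medical condition" likely to affect safety or to be incompatible with study procedures, and unresolved symptoms after a replacement could well qualify. Item 1 removes anyone unable to take part in procedures, and item 7 anyone with an MRI contraindication. Item 22 lists "Presence of local infection, vasculitis, burn, open wound, or bone fracture on any limb" where it would prevent treatment. Items 27 and 31 (exercise regimen, lying supine) may catch a few more. Item 25 bars "Presence of any of the contraindications for using the Renew™ NCP-5 device". Section 3.1, discussing MRI, says in mandatory terms that people with metallic parts in their bodies will be excluded; applied literally to an implant containing metal, that removes the patient whatever item 13 says. This also stands in good part. Its limits are that item 6 turns on an opinion, item 22 needs a specific lesion, and the contraindication list behind item 25 is not in this document. The remark on metal would make the replacement clause redundant if it were really applied that way.

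Third, the 3-month limb lacks its own reference date, and a reader might make that a second defect. It is not worth one. The words fixing the six-week limit to treatment can naturally be read across the whole item, and the catheterization limb has no separate date either.

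A reader might also infer that item 13 lets unrecovered joint replacement patients into the trial generally. The protocol does not support that: the general surgery limb bars all of them for the first six weeks, and the provisions above may catch many of the rest.

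**Conclusion.** The wording is wrong, within narrow limits. For replacements between six weeks and 3 months before first treatment, item 13 taken literally excludes recovered patients and does not itself exclude unrecovered ones. The window is 47 to 50 days, assuming that both limits count back from first treatment. Few subjects are likely to fall in it, though the protocol gives no number.

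The practical effect is a small eligibility and safety error, softened by the overlapping exclusions, by the sense most investigators would read into the clause, and by section 7.5, under which the operator raises pressure progressively while assessing discomfort. Nothing here shows that an unsuitable patient would in fact be treated. The endpoint, sample size, error rates and analysis are untouched. It is still worth correcting, because this is an operative safety criterion and the correction is very cheap.

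**What to change.** In the joint replacement limb of item 13, replace *as long as* with *unless* and leave the rest of the rider unchanged, so that a replacement in the last 3 months excludes the patient unless recovery is complete. While editing, repeat after the 3-month limit the before-treatment anchor that the six-week limb already uses. Keep the six-week limit for any surgery.

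If the sponsor intends a full 3-month exclusion regardless of recovery, delete the rider altogether. There is no need to add an exclusion reaching beyond 3 months; item 13 contains none, and that would be new policy.

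The cost is a one-clause amendment and a memo to sites. As it bears on patient safety, section 10.1 requires IRB approval before implementation. Sample size, endpoints and analysis do not change.
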